6 STATISTICAL ANALYSIS

6.1 Layout

The number of active doctors (oncologists) will be described.

The number of patients included and the number of patients followed up will be described by group (Cases/Controls).

The number of patients per visit, the time interval (in months) between inclusion and the follow-up visit for each visit (continuous) and the total duration of follow-up (in months) will be described per group (Cases/Controls).

6.2 Description of doctors

Study population: Population of active doctors

The characteristics of active doctors will be described overall:

- Age (years);
- Sex (male/ female);
- Type of practice (Hospital/Surgery/Independent);
- Sector of approval (Sector 1 / Sector 2 - Registered doctor charging private fees / Sector 3 - Not approved).

The characteristics of the sample of oncologists (age, sex, type of practice) will, if possible, be compared with those of the national database to ensure that the sample is representative.

6.3 Description of patients at inclusion

6.3.1 Demographical characteristics

Study population: Population of patients included

The demographic characteristics of the patients will be described by group and compared:

- Age (years);
- Sex (male/ female);
- Height (cm);
- Weight (kg).

6.3.2 Other characteristics

Study population: Population of patients included

The demographic characteristics of the patients will be described by group and compared:

- Time of diagnosis of metastatic renal cell carcinoma;
- Nephrectomy (Yes/ No)*;
If Nephrectomy:
 - Extended or partial;
 - With or without adrenalectomy;
 - With or without curettage;
 - Open or laparoscopic approach;
 - Time between diagnosis of metastatic renal cell carcinoma to nephrectomy (in months);

- Pathological classification (Clear cell carcinoma / Papillary carcinoma / Chromophobe carcinoma / Bellini duct carcinoma / Medullary carcinoma / Sarcomatoid carcinoma / Other);
A list of other classifications will be presented.
- TNM classification (T / N / M and TNM);
- Tumour size (mm);
- Furhamn nuclear grade (I / II / III / IV);
- Necrosis (Yes/ No)*;
- Pulmonary embolism (Yes/No)*;
- Sarcomatoid component (Yes/No)*.

** For these qualitative variables, the odds ratio (Case versus Control) will be presented.*

The demographic characteristics of the patients, at initiation of Sunitinib, will be described by group and compared:

- Time between diagnosis of metastatic renal cell carcinoma and initiation of Sunitinib (in months);
- Location of metastases:
 - Lung (Yes/ No);
 - Bones (Yes/No);
 - Liver (Yes/ No);
 - Adrenal glands (Yes/No);
 - Pancreas (Yes/No);
 - Brain (Yes/No);
 - Lymph nodes (Yes/No);
If Lymph nodes:
 - Supra-diaphragmatic (Yes/No);
 - Sub-diaphragmatic (Yes/No);
 - Recurrence at nephrectomy site (Yes/No) ;
 - Other (Yes/ No);
A list of the other locations will be presented.
- Number of metastatic sites;
- MSKCC prognostic classification (Good prognosis/Intermediate prognosis/Poor prognosis).

The characteristics of the patients in CR will be described for the Cases:

- Time between Sunitinib initiation and CR (years);
- Method of achieving the CR (Medical treatment alone/Combined with local treatment);
If combined:
 - Surgery (Yes/No);
 - Radiotherapy (Yes/ No);
 - Radiofrequency (Yes/ No);
 - Cryoablation (Yes/ No);
 - Metastasectomy (Yes/ No);
 - Other (Yes/ No);

A list will be presented of local treatments including dates of treatment, time between the diagnosis of metastatic renal cell carcinoma and local treatment and sites exposed.

- Radiological assessment of the CR:
 - Disappearance of all known target lesions (Yes/No);
 - Disappearance of all non-target lesions (Yes/No);
 - No new lesions (Yes/No);
 - All target and non-target lymph nodes <10 mm (Yes/No);
- Therapeutic strategy after CR (Continuation of Sunitinib treatment/Discontinuation of Sunitinib treatment).

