8.1.3. Obtaining of patient's informed consent

An informed consent form, accompanied by a patient information leaflet in which the purpose of the blood samples collected will be clearly stated, will be signed by each patient before any data collection.

In addition, it will be mentioned that the histological samples taken at the diagnosis of the patients will be collected in order to constitute a bank of samples

A second informed consent form specific to the genetic analyses will be signed by each patient prior to all sampling.

8.1.4. Data collected in the individual case report form for each patient included (Appendix 3)

A) Data relating to the physician

- Surname, first name
- Gender
- Age
- Zip code, Town
- Public or private practice
- Type of contract

B) Screening form (only for cases)

- Visit screening date
- Consentment sign date
- Inclusion and non inclusion criteria
- Demographic data: month and year of birth (MM/AAAA)
- Data relating to the initial treatment of the patient: date of diagnosis of the initial renal cancer, date of diagnosis of renal cell carcinoma
- Data relating to the status of the patient in complete remission: Sunitinib start date, number and localization of metastatic sites at initiation of Sunitinib
- Blood samples during the screening visit: yes / no sampling and date of collection. If the samples are not available during the screening visit, a period of 6 weeks between screening and sampling will be allowed.
- Histological samples: date of sampling, type of sample, method of fixation.

C) Data collected at inclusion

For the cases

- Demographic data: age, gender, height, weight
- Data on the diagnosis of patients with metastatic renal cancer in complete remission: date of initial diagnosis of kidney cancer, date of diagnosis of metastatic renal cell carcinoma, nephrectomy (Yes / No), date of nephrectomy, type of nephrectomy; fixation method, OMS pathological classification, TNM classification 2009, Furhman nuclear grade, presence of necrosis, tumor size, presence or absence of a sarcomatoid embolus component
- Data relating to the state of the patient in CR at initiation of Sunitinib: initiation date, location of metastases, number of metastatic sites, prognostic classification MSKCC

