8.2.3. Inclusion criteria

- Adult patients (≥ 18 years)
- Patients with mRCC confirmed by histological analysis
- Treated with Sunitinib according to a regimen in the text of the SmPC
- Presenting a complete remission in the preceding 5 years (according to RECIST v1.1) with Sunitinib only or combined with localized treatment (surgery, radiotherapy, cryoablation or radiofrequency ablation)
- Patients of childbearing age using a mandatory method of contraception
- Affiliated to a social security scheme
- Informed about the study methods and having given their consent

Exclusion criteria

- Complete remission occurring in the absence of treatment with Sunitinib

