2.5 Number of patients required

The primary objective of the study is to describe the characteristics of mRCC patients achieving a CR with Sunitinib (Cases) and to compare them to the characteristics of metastatic renal cell carcinoma patients not achieving a CR with Sunitinib to identify factors associated with the occurrence of complete remission.

A sample size of N = 40 cases and N = 80 controls will provide a power of 80% in the detection:

- For continuous variable with a normal distribution, of an effect size (Cohen's d) ≥ 0.55 ;
- For a dichotomous variable, of a frequency difference between cases and controls corresponding to the ORs presented in the table below:

Frequency in controls	10%	20%	30%	40%	50%	60%	70%	80%	90%
Odds Ratio	≥ 4.33	≥ 3.27	≤ 0.19 or ≥ 3.16	≤ 0.26 or ≥ 3.12	≤ 0.29 or ≥ 3.44	≤ 0.32 or ≥ 3.78	≤ 0.32 or ≥ 5.29	≤ 0.31	≤ 0.23

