4 GENERAL CONSIDERATIONS FOR THE STATISTICAL ANALYSIS OF THE DATA

4.1 Statistical methods

The biostatistics department at AXIAL will perform the statistical analysis, with the exception of the analysis of biological data and biomarkers. Data will be analysed using SAS® software (version 9.4 or later - SAS Institute, North Carolina, USA).

Statistical tests will be carried out bilaterally at a 5% significance level (alpha).

Results will be presented in the form of tables per group (Cases/Controls) presenting:

- For quantitative parameters: number of patients (n), mean and standard deviation, minima and maxima, median and quartiles, and number of missing values.
- For qualitative parameters: number of patients, absolute and relative frequencies for each parameter modality, and number of missing values. Missing data will not be considered when calculating percentages.

Quantitative parameters will be compared between groups using the following methods: Beforehand, the distribution of the parameter will be checked graphically and by using Skewness and Kurtosis and Shapiro-Wilk statistics. If the distribution is considered normal, groups will be compared using a Student's t-test and the difference in means and the 95% Confidence Interval (CI) will be presented. If this is not the case, groups will be compared using a Wilcoxon rank sum test and Hodges-Lehmann estimator, with a presentation of the 95% CI.

For non-ordinal qualitative variables, groups will be compared using the Chi-2 test (or Fisher's exact test if the theoretical numbers <5) and the odds ratio will be presented when specified.

For ordinal qualitative variables, groups will be compared using the Cochran-Mantel-Haenszel test, ridit modified scores ('row mean score differ'). For ordinal qualitative count variables, groups will be compared using the Cochran-Mantel-Haenszel test, 'row mean score differ' table option.

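### SAP 6.3.2 compares nephrectomy between Cases and Controls without dating it against Sunitinib start, so surgery done after that start can count in Cases but not in Controls

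*SAP*

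**What the plan says.** SAP 6.3.2 has two lists of characteristics to be compared between groups.

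- The first has no time reference beyond inclusion. It contains "Nephrectomy (Yes/ No", starred for a Case-versus-Control odds ratio, with the type of nephrectomy and the time from metastatic diagnosis to nephrectomy nested under it. It also holds tumour size, "Necrosis (Yes/ No" and the sarcomatoid component.
- The second is expressly tied to Sunitinib initiation. It holds the time from metastatic diagnosis to Sunitinib, the metastatic sites and the MSKCC class. Nephrectomy is not in it.

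The only nephrectomy interval derived in SAP 5.2 starts at metastatic diagnosis.

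For Cases, protocol 8.2.3 accepts a CR within the preceding 5 years, reached "with Sunitinib only or combined with localized treatment (surgery, radiotherapy, cryoablation or radiofrequency ablation". SAP 2.3 allows inclusion only after central scan review has validated the CR. Protocol 8.1.4 C then collects "nephrectomy (Yes / No), date of nephrectomy, type of nephrectomy" among the diagnosis data.

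For Controls, SAP 2.3 places inclusion at Sunitinib initiation, and protocol 8.2.4 requires no earlier Sunitinib. The Control pages in Appendix 6 for 6 months, 12 months, progression and 36 months contain no nephrectomy field.

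**The concern.** The primary objective is to identify factors associated with CR. A factor in that sense should be fixed before treatment starts, or at least be observed over the same period in both groups. Nephrectomy as defined meets neither condition. The observation window closes at Sunitinib start for a Control. For a Case it stays open through treatment, through any surgery that helped to achieve the CR, and for up to 5 years afterwards.

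Surgery offered because a patient was responding, or performed to remove the last disease, could then be reported as a characteristic associated with CR. The nested comparison of time from metastatic diagnosis to nephrectomy has the same asymmetry, since it is cut off near Sunitinib start in Controls only.

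**Working it through.** **Step 1. Reproduce the plan's power statement.** SAP 2.5 says: "A sample size of N = 40 cases and N = 80 controls will provide a power of 80% in the detection" of the stated effects. SAP 4.1 says: "Statistical tests will be carried out bilaterally at a 5% significance level (alpha".

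- Continuous, "effect size (Cohen's d) ≥ 0.55": power = Φ(d·√(n₁n₂/(n₁+n₂)) − 1.96) = Φ(0.55 × √(40×80/120) − 1.96) = Φ(2.84 − 1.96) = 81.1%. The noncentral t gives 80.4%.
- Binary, 70% in Controls, "≤ 0.32 or ≥ 5.29": the upper bound corresponds to 37/40 = 92.5% of Cases, since (0.925/0.075)/(0.70/0.30) = 5.29. Pooled-variance power there is 84.3%. One Case fewer (36/40, OR 3.86) gives 71.4%.

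The power statement reproduces. It does not bear on the time reference, but it gives a scale for the figures below.

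**Step 2. Trace when the field is filled.**

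| | Cases | Controls |
|---|---|---|
| Field completed | After validated CR | At Sunitinib initiation |
| Surgery possible between Sunitinib start and entry | Yes; local surgery is allowed as part of the CR | No |
| Later nephrectomy can reach the compared variable | Yes | No; no field on later pages |
| SAP rule separating surgery before and after Sunitinib | None | None needed at entry |

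If a Control reaches CR and moves to the Case group, the documents do not say whether the nephrectomy field is updated.

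**Step 3. Illustrate the size.** The documents give neither the nephrectomy rate before Sunitinib (p) nor the share of remaining Cases operated on afterwards (f). Both are assumptions here. Take p equal in the two groups, so the true OR is 1.

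- Apparent Case rate: q = p + (1 − p)f.
- Apparent OR: [q/(1 − q)]/[p/(1 − p)].
- Example, p = 0.70 and f = 0.25: q = 0.70 + 0.30 × 0.25 = 0.775. OR = (0.775/0.225)/(0.70/0.30) = 1.48. This is 40 × 0.30 × 0.25 = 3 Cases.

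The rejection rate comes from exact enumeration of two binomials (40 and 80) with the SAP's test: chi-square, or Fisher if an expected count is below 5, two-sided 5%. Entries are apparent OR and chance of p < 0.05.

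| p | f = 0 | f = 10% | f = 25% | f = 50% |
|---|---|---|---|---|
| 50% | 1.00; 4.6% | 1.22; 7.5% | 1.67; 24.3% | 3.00; 76.2% |
| 60% | 1.00; 5.0% | 1.19; 6.9% | 1.56; 18.5% | 2.67; 60.9% |
| 70% | 1.00; 5.0% | 1.16; 6.1% | 1.48; 13.2% | 2.43; 43.9% |
| 80% | 1.00; 4.9% | 1.14; 5.2% | 1.42; 8.7% | 2.25; 25.8% |
| 90% | 1.00; 3.3% | 1.12; 3.0% | 1.37; 3.5% | 2.11; 7.2% |

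At f = 10% the test stays near its nominal level. At p = 70%, f would have to reach 75% (9 of 40 Cases) for the artefact to equal the OR of 5.29 in the SAP's table. Counting only nephrectomies before Sunitinib restores the f = 0 column.

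**The case against.** The best contrary evidence is the Case report form in Appendix 5. It prints the nephrectomy and histology fields under a heading about the patient's status at the start of Sunitinib. A site that takes the heading literally would enter only earlier surgery, and the asymmetry would disappear. This stands in part. But protocol 8.1.4 C and SAP 2.3 file the same field under diagnosis data, the Control form files it under initial treatment, and none of them tells sites to leave out later surgery. At best, sites may differ in what they enter.

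It can also be said that surgery contributing to the CR is already handled, because SAP 6.3.2 lists local treatments for Cases with dates and sites. The rationale, moreover, speaks of residual metastasectomy, not nephrectomy. That is fair, but a generic surgery box sits beside the metastasectomy box, and nothing prevents the same operation from also being a yes in the nephrectomy field.

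Two stronger readings are tempting and are not supported.

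- A reader might infer that reverse causation has been shown. The documents do not say that any Case had a nephrectomy after starting Sunitinib.
- A reader might infer that necrosis or tumour size in Cases was read on Sunitinib-exposed tissue. The documents do not say which specimen was read, and a diagnostic biopsy is possible. Protocol 8.1.3 describes the banked tissue as taken at diagnosis, although Appendix 14 only requires sampling before the screening visit, which for Cases follows the CR. The printed Case form shows no tumour-size field at all.

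**Conclusion.** The point holds as a defect in how a starred factor of the primary objective is defined. Followed as written, the SAP can count nephrectomy after Sunitinib start in Cases and cannot count it in Controls. The direction of the bias is towards a spurious positive association with CR.

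Its size cannot be determined from the documents. Over assumed base rates of 50% to 90%, it is negligible if 10% or fewer of the remaining Cases were operated on later (OR 1.12 to 1.22, rejection 3% to 8%). It becomes material at a 50% share, with an OR of 2.11 to 3.00 and rejection of 7% to 76%. These figures rest on equal rates before Sunitinib in the two groups and on sites recording later nephrectomies in the Case field.

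For histology the documents support only a check by sensitivity analysis.

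**What to change.** In SAP 5.2 and 6.3.2:

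1. Define the compared factor as nephrectomy dated before Sunitinib initiation (yes/no). Restrict the compared type and timing to those nephrectomies.
2. List nephrectomies after initiation descriptively, with the Cases' other local treatments.
3. Add an ordering rule for incomplete dates. Setting a missing day to the first of the month can reverse two dates in the same month, and no rule covers a missing nephrectomy month. One workable rule is to order on the known parts of the dates where they suffice and query the site otherwise. Where the order stays unresolved, report the comparison under both assignments.
4. For necrosis, sarcomatoid component and tumour size, flag Cases whose only nephrectomy is dated after Sunitinib start and repeat the comparison without them. A restriction by specimen date is not feasible for all patients, because the forms date only the banked sample, which is optional.

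The cost is SAP wording, one derived variable, one date rule and one sensitivity analysis. The nephrectomy and Sunitinib start dates are on both case report forms, so no new data field is needed. Some date queries may be.

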- Medullary cell carcinoma		
- Sarcomatoid contingent		
- Other		

(please specify):
- TNM classification: T |____| N |____| M |____|
- Fuhrman nuclear grade: I |____| II |____| III |____| IV |____|
- Presence of necrosis?

YES	NO
	
- Vascular embolism

YES	NO
	

**DATA RELATING TO THE STATUS OF A PATIENT IN COMPLETE REMISSION
AT START OF SUNITINIB**

Sunitinib start date |_____|_____|_____|_____|2|0|1|____| (dd/mm/yyyy)

METASTATIC SITES		
LOCALIZATION OF METASTASES	YES	NO
- Lungs		
- Bone		
- Liver		
- Adrenal glands		
- Pancreas		
- Brain		
- Lymph nodes		
o Supradiaphragmatic		
o Infradiaphragmatic		
- Recurrence at the nephrectomy renal bed		
- Other		
(please specify):		

NUMBER OF METASTATIC SITES: |____|

MSKCC PROGNOSTIC CLASSIFICATION		
 Good prognosis (0 pejorative factors)		
 Moderate diagnosis (1 or 2 pejorative factors)		
 Good diagnosis (more than 2 pejorative factors)		

DATA RELATING TO COMPLETE REMISSION

Complete remission date |_____|_____|_____|_____|2|0|1|____| (dd/mm/yyyy)

• Complete remission obtained by:	YES	NO
- Medical treatment only		
- Combined with localized treatment		
If yes:		
o Surgery		
o Radiotherapy		
o Radiofrequency		
o Cryoablation		
o Metastasectomy		
o Other		

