		Site:

RADIOLOGICAL ASSESSMENT OF THE COMPLETE REMISSION (RECIST v 1.1 criteria)

	YES	NO
- Disappearance of all known target lesions		
- Disappearance of all non-target lesions		
- No appearance of new lesions		
- All target or non-target lymph nodes < 10 mm		

TREATMENT STRATEGY FOLLOWING COMPLETE REMISSION

	YES	NO
- Continuation of Sunitinib treatment		
- Discontinuation of Sunitinib treatment		

SAMPLING BEFORE START OF SUNITINIB*** A delay of 6 weeks is tolerated between initiation and sampling**

	YES	NO
- Blood sample of 2 times 5 ml		
Sampling date ____ ____ ____ ____ ____ ____ (dd/mm/yyyy)		
Histological sample of primitive tumor		
Sampling date ____ ____ ____ ____ ____ ____ (dd/mm/yyyy)		

ANNUAL VISIT FOLLOWING A CR

Visit date | | | | | | | | | | | | (jjmmaaaa)

If a Sunitinib complementary treatment (pseudo adjuvant) is realised since the CR, could you indicate the duration | | | | (month)

Disease State

• Desease evolution :

- Complete Response
- Partial Response
- Progression (Thanks to complete the disease follow-up visit)
- Stabilisation
- No evaluated

Modification treatmentt.

• Sunitinib treatment always on going :

Actual dosage; | | | | , | | | | mg / j

Actual schema : 4/2
2/1
Continuous
Other

• Sunitinib temporary cessation:

Sunitinib temporary cessation duration | | | | (days)

Sunitinib cessation date: | | | | | | | | | | | | (jjmmaaaa)

Temporary cessation Reason: Progression
Intolérance (Thanks to complete Adverse Event form)

Complete Response
Local treatment
Other

.....
Has the sunitinib been taken back? Yes No

If yes, Sunitinib recovery date | | | | | | | | | | | | (jjmmaaaa)

Définitive Cessation

Sunitinib cessation date : | | | | | | | | | | | | (jjmmaaaa)

Cessation reason : Progression
Intolerance (Thanks to complete Adverse Event form)
Complete Response Retention
Doctor / Patient choice
Other

DISEASE PROGRESSION VISIT FOLLOWING A CR

Visit date |_____|_____|_____|_____|2|0|1|____| (dd/mm/yyyy)

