5.2 Derivative data

The following variables will be calculated:

- Interval between visit X and inclusion (in months):
(Date of follow-up visit X - Date of inclusion visit) / 365.25 x 12.
- Total length of follow-up (in months):
(Maximum date between Date of last visit or Date of last news or Date of death - Date of inclusion visit) / 365.25 x 12.
Note: In case of incomplete dates (date of last news or date of death):
If the day is missing, it will be replaced by the first day of the month.
If the month is missing, it will be replaced by the month of January.
If the date completed is earlier than the last visit carried out, then the date will be replaced by the last visit carried out.
- Age (in years):
Year of inclusion – Year of birth.
- Time of diagnosis of metastatic renal cell carcinoma (in years):
(Date of inclusion visit - Date of diagnosis of metastatic renal cell carcinoma) / 365.25.
Note: In case of incomplete dates (date of diagnosis of metastatic renal cell carcinoma):
If the day is missing, it will be replaced by the first day of the month.
If the month is missing, only the year will be used.
- Time from diagnosis of metastatic renal cell carcinoma to nephrectomy (in months):
(Date of nephrectomy - Date of diagnosis of metastatic renal cell carcinoma) / 365.25 x 12
Note: In case of incomplete dates (date of nephrectomy or date of diagnosis of metastatic renal cell carcinoma):
If the day is missing, it will be replaced by the first day of the month.
- Time between diagnosis of metastatic renal cell carcinoma and initiation of Sunitinib (in months):
(Date of Sunitinib initiation - Date of diagnosis of metastatic renal cell carcinoma) / 365.25 x 12
Note: In case of incomplete dates (Sunitinib initiation date or date of diagnosis of metastatic renal cell carcinoma):
If the day is missing, it will be replaced by the first day of the month.

For Cases:

- Time between diagnosis of metastatic renal cell carcinoma and local treatment (in months):
(Date of local treatment - Date of diagnosis of metastatic renal cell carcinoma) / 365.25 x 12
Note: In case of incomplete dates (date of local treatment or date of diagnosis of metastatic renal cell carcinoma):
If the day is missing, it will be replaced by the first day of the month.
-

- Time between Sunitinib initiation and CR (in years):
(Date of CR - Date of Sunitinib initiation) / 365.25.
*Note: In case of incomplete dates (date of CR or date of Sunitinib initiation):

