Patient follow-up data will be described for the cases at the end-of-study visit:

- Best objective response observed after progression (Complete / Partial / Progressive / Stabilised);
- Duration of treatment received after progression with first-line Sunitinib (months);
- Early termination of the study (Yes/No);
- Response achieved (persistent CR since inclusion visit / CR after treatment of recurrence / Disease progression);
- Number of subsequent treatment lines from progression, post CR;
- Death (Yes/ No).

Progression-free survival at the end of the study will be analysed using the Kaplan Meier method, with a presentation of the survival curve. The progression-free survival rate will be estimated with a 95% confidence interval.

6.5 Description of follow-up visits for mRCC patients treated with first-line Sunitinib, non CR (Controls)

Study population: Population of followed-up patients - Controls

Patient follow-up data will be described for the controls at 6 and 12 months of treatment:

- Sunitinib dose (50 mg / 37.5 mg / 25 mg);
- Current regimen (4/2 / 2/1 / Continuous);
- Clinical assessment (Complete Response / Partial Response / Stable Disease / Progression);
If Partial Response:
 - Percentage of tumour reduction (%)
- Location of metastases:
 - Lung (Yes/ No);
 - Bones (Yes/No);
 - Liver (Yes/ No);
 - Adrenal glands (Yes/No);
 - Pancreas (Yes/No);
 - Brain (Yes/No);
 - Lymph nodes (Yes / No); If Lymph nodes:
 - Supra-diaphragmatic (Yes/No);

- Sub-diaphragmatic (Yes/No);
- Recurrence at nephrectomy site (Yes/No) ;
- Other (Yes/ No);
A list of the other locations will be presented.
- Number of metastatic sites;

Patient follow-up data will be described for the controls at the time of the progression:

- Time between initiation of treatment and progression (in months);
- Type of progression (Local Progression/Distant Progression);
If distant progression, at which level (at a known metastatic site/new metastatic site);
- Location of metastases:
 - Lung (Yes/ No);
 - Bones (Yes/No);
 - Liver (Yes/ No);
 - Adrenal glands (Yes/No);
 - Pancreas (Yes/No);
 - Brain (Yes/No);
 - Lymph nodes (Yes / No); If Lymph nodes:
 - Supra-diaphragmatic (Yes/No);
 - Sub-diaphragmatic (Yes/No);
 - Recurrence at nephrectomy site (Yes/No) ;
 - Other (Yes/ No);
A list of the other locations will be presented.
- Number of metastatic sites;

Patient follow-up data will be described for the controls at the end-of-study visit:

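### The printed Case CRF contradicts Protocol 8.1.4 and the SAP: tumour size has no Case field, and sarcomatoid status and progression timing can only be approximated

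*SAP*

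**What the plan says.** SAP 6.3.2 compares the included Cases and Controls on a list of characteristics. The list contains "Tumour size (mm" and, with an odds ratio, "Sarcomatoid component (Yes/No". The sarcomatoid component is listed in addition to a sarcomatoid category in the pathological classification. For Cases who had local treatment, the same section promises this: "A list will be presented of local treatments including dates of treatment". SAP 5.2 derives an interval from "Date of local treatment - Date of diagnosis of metastatic renal cell carcinoma". It also defines time from CR to progression and Case progression-free survival (PFS), both using the date of progression.

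Protocol 8.1.4 lists for Cases at inclusion "presence of necrosis, tumor size, presence or absence of a sarcomatoid embolus component", wording that runs the embolus and sarcomatoid items together. It also lists the date of progression, separately from the visit date. SAP 2.3 repeats tumour size, sarcomatoid component and date of progression for Cases. Neither list includes a date of local treatment.

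The printed Case form in Appendix 5 ends its histology block with TNM, Fuhrman grade, "Presence of necrosis" and vascular embolism. Its page headed "DISEASE PROGRESSION VISIT FOLLOWING A CR" has a visit date and no other date for the progression.

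**The concern.** Comparing Cases with Controls is the primary objective, so each compared characteristic needs the same field in both groups. If sites complete Appendix 5 as printed, tumour size exists for Controls only. Sarcomatoid status rests on one item for Cases and two for Controls. Case progressions have no date of the kind that SAP 5.2 requires. Any repair chosen after the data have been seen would be an unplanned analytic decision, and it could bring tumour size into the two groups by different routes.

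**Working it through.** **1. Fields side by side.**

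| Item | Use in SAP | Listed for Cases in Protocol 8.1.4 / SAP 2.3 | Case form (App. 5) | Control form (App. 6) |
|---|---|---|---|---|
| Tumour size | 6.3.2, compared | yes / yes | absent | present, in mm |
| Sarcomatoid component | 6.3.2, compared, odds ratio | yes / yes | pathology tick only (*Sarcomatoid contingent*, Yes/No) | same tick plus a separate item |
| Date of progression | 5.2 and 6.4, time from CR and PFS | yes / yes | visit date only | visit date and progression date |
| Date of local treatment | 5.2 interval, 6.3.2 listing | no / no | Yes/No and site only | not needed |

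There is one gap in the other direction. SAP 6.5 reports for Controls "Type of progression (Local Progression/Distant Progression", the same wording as for Cases in 6.4, but the Control form records only progression at a known site or at a new site.

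**2. What each absence does.**
- Tumour size: no Case values, so no comparison.
- Sarcomatoid component: the tick is on both forms, so a 2×2 table and odds ratio can be formed from it. The SAP does not name it as the variable.
- PFS: the Case form holds the CR date, date of death and latest-information date, so deaths and end-of-study censoring can be dated. Only progression events lack their specified date, and the progression-visit date is the nearest substitute. Time from CR to progression is affected in the same way.
- Local-treatment date: affects one Case-only listing and one derived interval.

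**3. Does the SAP supply a substitute?** SAP 5.1 replaces no missing data except where later sections say so. For progression, the exception in 5.2 fills in a missing day. It does not cover a progression date that was never recorded.

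**4. Share of the primary comparisons.** SAP 6.3.1 has 4. SAP 6.3.2 has 17 in its first list (T, N, M and TNM counted separately) and 14 at Sunitinib initiation: 4 + 17 + 14 = 35. On the printed form, one of the 35 (tumour size) has no Case data and one (sarcomatoid component) needs a substitute item.

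**5. Power if tumour size is only partly recovered.** Inputs from SAP 2.5 and 4.1: 40 Cases, 80 Controls, d = 0.55, two-sided 5%. Two-sample t test, noncentrality = d / √(1/n₁ + 1/n₀).
- Plan's own figure: √(1/40 + 1/80) = 0.194, noncentrality 2.84, power 80.4%, detectable d 0.547. This reproduces the stated 80% at 0.55.
- 30 Cases: √(1/30 + 1/80) = 0.214, noncentrality 2.57, power 72%, detectable d 0.61.
- 20 Cases: √(1/20 + 1/80) = 0.250, noncentrality 2.20, power 59%, detectable d 0.71.
- 10 Cases: √(1/10 + 1/80) = 0.335, noncentrality 1.64, power 37%, detectable d 0.95.

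The recovery counts are assumptions. The documents give none.

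**The case against.** The strongest reply is that Appendix 5 is not the working instrument. Data are entered in an eCRF that is not supplied. Under Protocol 8.2.5.4 the company that configures the eCRF also writes the SAP, and both texts list three of the four items for Cases. The printed form is also visibly unreliable in other places. Sample type and fixation, listed for the screening visit, are not on its screening page. The 36-month visit year is pre-printed for the 2010s although follow-up runs to December 2021. The worst MSKCC box is labelled as good. All of this stands: absence from the appendix does not prove that the data were not collected. It does not remove the contradiction, because Appendix 5 is the protocol's own Case form. It also gives no cover for the local-treatment date, which neither collection list contains.

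Two stronger readings are tempting, and the documents support neither. A reader might infer that two primary comparisons and Case PFS cannot be computed at all. The shared sarcomatoid tick and the recorded visit, death and CR dates rule that out; only tumour size is wholly absent. A reader might also infer from the 2-to-3-month visit spacing that Case progressions would be dated up to about 3 months late. Protocol 8.1.4 ties the Case progression form to the visit at which progression is diagnosed, so the visit date may lie close to detection. Visit spacing creates uncertainty about detection in both groups. It does not measure the gap between a recorded progression date and the diagnosing visit, and the documents give no figure for that gap.

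It is also fair to say that Case PFS is a descriptive Kaplan-Meier estimate with no planned test against Controls, and that the local/distant item for Controls is descriptive and minor.

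**Conclusion.** The point holds as a contradiction between the printed Case form on one side and Protocol 8.1.4, SAP 2.3 and the Control form on the other. The local-treatment date is a separate gap between the form and SAP 5.2 and 6.3.2. The consequences differ by item: the tumour-size comparison is not possible on that form, the sarcomatoid odds ratio and the Case progression times depart from their specification, and the local-treatment date touches description only. Using the visit date would lengthen Case PFS wherever progression was established before the visit, by an amount the documents do not let us state. All of this assumes that the eCRF matches Appendix 5. If it holds the fields, what remains is to correct the appendix and close any gap on the local-treatment date. The power figures further assume roughly normal tumour size and Cases missing at random. The mismatch should be settled before database freeze.

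**What to change.** 1. Check the operative eCRF against SAP 5.2, 6.3.2 and 6.4, and correct Appendix 5 to match.
2. Where fields are absent, add tumour size (mm), date of progression and date of each local treatment for Cases. Back-fill them from pathology reports and charts before database freeze, and report how many Cases were recovered.
3. Use one identical histology block in both groups, or state in the SAP that the shared sarcomatoid tick is the sarcomatoid variable for both.
4. State in SAP 5.2 that the progression-visit date is used only when the progression date is missing, and report how often that happens.
5. Add local/distant progression to the Control form, or drop it from SAP 6.5.

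Cost: a form update, an SAP clarification and site queries for at most 40 Cases, plus Control queries if the local/distant item is added.
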